Study Title: Study of Time-restricted Eating on Weight Loss. A Randomized Controlled Trial of the Effects of Time-restricted Eating on Weight Loss in Obese Subjects.

NCT: 03393195

Date: May 14th, 2019

Experimental Design:

This is a pilot study to examine the metabolic effects of TRF in overweight/obese humans. 100+ overweight/obese (BMI>27, <43kg/m²) male and female subjects over the age of 18 will be recruited to participate in this study. Participants will receive an iHealth Bluetooth connected scale to use during the study. Participants will be randomized to one of two eating plans. 1) **8-hour eating window:** TRF group instructed to limit daily calorie intake between 12:00pm and 8:00pm each day (only water and black coffee/tea permitted outside of eating window); or 2) **Consistent meal timing:** participants are instructed to eat three structured meals each day during specified eating windows (7:00am-11:00am, 11:00am-3:00pm, 4:00pm-10:00pm) Group allocation will be provided to subjects using the Eureka mobile research platform, and no recommendation on total calorie or macronutrient intake was provided. Participants will be instructed to use their iHealth scales daily, preferably in the morning before their first meal (Table 1). The Eureka app will also send adherence surveys, sleep questionnaires, and food attitude surveys to participants throughout the study.

Participants who live within 60 miles of UCSF were invited to participate in in-depth metabolic testing at UCSF. Immediately prior to study start, participants will go to the Clinical and Translational Science Institute (CTSI) clinical research center at the University of California, San Francisco (UCSF) in order to collect baseline values for the measurements listed in Table 2. Since fasting glucose and insulin measurements will be collected, participants will be instructed to fast from 8:00pm the night before. Additionally, iPhone users will be given the option to use the Oura ring for sleep and activity tracking. After 12 weeks, participants will come to the CTSI clinic to repeat the baseline measurements.

Table 1. Measurements to be collected by subjects at home.

Measurement	Mode of Collection	Frequency
Weight	Bluetooth Scale	Daily
Adherence Survey	Eureka	Daily
Sleeping habits (PSQI)	Eureka	Monthly
Food Attitudes (RED Scale)	Eureka	Monthly

Table 2. Measurements to be acquired at baseline and 12-week follow-up (local subjects only)

Questionnaire: Age, Sex, Ethnicity, SES, BMI,

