The primary outcome will be percent change in weight since baseline, measured daily via iHealth, in the overall cohort of 100 participants. To estimate the intention-to-treat effect of treatment assignment, we will use a linear mixed model (LMM) with fixed effects for treatment assignment, days since baseline (as a continuous variable), and their interaction, and random effects for participant and day, with unstructured covariance matrix. The treatment effect will be estimated by the fixed effect for the treatment by day interaction, capturing the between-group divergence in weight loss trajectories. In sensitivity analyses, we will repeat the analysis after Winsorizing outliers, which will be defined as points more than 1.5 times the interquartile range below the 25th or above the 75th percentile of the overall distribution. No adjustment will be made to p-values or confidence intervals for multiple comparisons for the primary outcome.

Our secondary outcomes will include body fat, lean mass, fasting glucose, insulin, and HbA1c levels, resting metabolic rate, and total energy expenditure, assessed at the baseline and 12-week clinical visits for a subset of 46 participants. To estimate the intention to treat effect of treatment assignment on changes in these outcomes, we will use LMMs with fixed effects for treatment assignment, an indicator for the 12-week visit, and their interaction, and a random effects for participant. The treatment effect will be estimated by the interaction. In sensitivity analyses, we will repeat these analyses Winsorizing any outliers, defined as in the primary analysis. P-values and confidence intervals will be Bonferroni-corrected for 7 comparisons.

All other outcomes measured at the baseline and 12-week clinical visits will be considered exploratory and analyzed using the methods described for the secondary outcomes, without penalization for multiple comparisons.

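### The planned model for body fat and lean mass ignores the daily home weights, so if missing the week-12 visit depends on weight change differently by arm, the effects on these outcomes are biased

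*Combined protocol and SAP*

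**What the plan says.** The Statistical Analysis Plan lists seven secondary outcomes: body fat, lean mass, fasting glucose, insulin, HbA1c, resting metabolic rate and total energy expenditure. They are "assessed at the baseline and 12-week clinical visits for a subset of 46 participants". The Experimental Design section confirms that there is a single follow-up clinic visit: "After 12 weeks, participants will come to the CTSI clinic to repeat the baseline measurements".

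The stated aim is "To estimate the intention to treat effect of treatment assignment on changes in these outcomes". The model has "fixed effects for treatment assignment, an indicator for the 12-week visit, and their interaction, and a random effects for participant", and "The treatment effect will be estimated by the interaction". P-values and intervals are Bonferroni-corrected for seven comparisons. The only sensitivity analysis is Winsorizing of outliers. There is no rule for a missed week-12 visit, no stated missing-data assumption and no imputation.

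Home weights are collected from everyone, including the local participants: "Participants will be instructed to use their iHealth scales daily, preferably in the morning before their first meal". The plan uses them only for the primary outcome, "percent change in weight since baseline, measured daily via iHealth, in the overall cohort of 100 participants".

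**The concern.** A mixed model allows for missing visits only through data that are in the model. Here that means the baseline value of the same outcome. It cannot see how a participant fared between baseline and a missed week-12 visit.

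In a weight-loss trial, where participants know their allocation and weigh themselves daily, progress may plausibly influence who returns to the clinic, and may do so differently in the two arms. If participants who did poorly stay away more often in one arm, that arm's mean change in fat mass looks better than it was, although the analysis is labelled intention-to-treat. Home weight is closely related to fat and lean mass and is already collected, so the plan leaves relevant information unused.

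**Working it through.** **The plan's own figures.** The subset size of 46 cannot be reproduced, because the documents give no alpha, power, effect size, SD or attrition rate for it. The Bonferroni count of 7 matches the seven outcomes listed.

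**What the planned model does with a missed visit.** Let ρ be the within-participant correlation implied by the random effect. In each arm the model's estimate of mean change is

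attenders' mean change + (1 − ρ) × (attenders' mean baseline − mean baseline of all in the arm).

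If attenders and non-attenders have similar baselines, the second term vanishes and the interaction is the difference in change among attenders. Simulation agrees: the planned model and an attenders-only comparison differed in bias by at most 0.003 SD whenever missingness was random or depended on weight change.

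**Size by hand (all inputs assumed).** Take 23 local participants per arm, with 5 on time-restricted eating and 2 controls missing week 12. Non-attenders' weight change is 2.5 kg worse, 70% of it fat, and the SD of fat change is 2.5 kg.

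- Fat difference: 0.70 × 2.5 = 1.75 kg.
- Bias, in favour of time-restricted eating: 1.75 × (5/23 − 2/23) = 1.75 × 0.130 = 0.23 kg.
- Standard error with all 46 measured: 2.5 × √(2/23) = 0.74 kg, so the bias is 0.31 standard errors.
- Standard error with the 18 and 21 who attend: 2.5 × √(1/18 + 1/21) = 0.80 kg, so the bias is 0.28 standard errors.

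**Size by simulation (all inputs assumed).** 23 per arm; true effect −0.4 SD of change, acting wholly through weight; baseline SD 3.2 times the change SD; correlation r between fat change and home-weight change of 0.5 or 0.8; 10% to 30% of visits missed overall; where attendance depends on weight, log-odds of missing rise by 1 per SD of home-weight change. Bias was taken from large samples. A negative value exaggerates the benefit of time-restricted eating.

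| Missed visits depend on | Bias of planned model, SD of change |
|---|---|
| nothing | about 0 |
| baseline, one arm | −0.02 to −0.04 |
| home-weight change, same in both arms | +0.03 to +0.06 |
| home-weight change, one arm, r = 0.5 | −0.04 to −0.10 |
| home-weight change, one arm, r = 0.8 | −0.08 to −0.18 |
| home-weight change, opposite directions, r = 0.5 | −0.09 to −0.25 |
| home-weight change, opposite directions, r = 0.8 | −0.15 to −0.40 |

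With all 46 measured, the standard error is √(2/23) = 0.29 SD.

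**Effect of using home weights.** Regression imputation of the missing change from arm, baseline and home-weight change brought the large-sample bias to within 0.01 SD. At n = 46, with dependence in one arm and r = 0.8:

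| Missed visits | Bias, planned | Bias, imputed | Sampling SD, planned | Sampling SD, imputed |
|---|---|---|---|---|
| 10% | −0.08 | −0.01 | 0.31 | 0.30 |
| 20% | −0.12 | +0.01 | 0.33 | 0.31 |
| 30% | −0.18 | +0.01 | 0.35 | 0.32 |

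When only half the weight path was seen, the planned model's bias was −0.04 to −0.10 SD and imputation still removed it. In all these runs attendance depended on weights that had been seen, which is the condition under which imputation works. They used single regression imputation, as a check on bias and spread rather than on interval coverage.

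**The case against.** **The bias is conditional.** A reader might infer that the secondary results will be biased by withdrawal. The documents do not support this: they give no attrition rate, no split by arm and no link between attendance and weight. An equal mechanism in both arms pulled the estimate slightly toward no effect, so a bias favouring one arm needs a differential mechanism that nothing in the text establishes. This objection stands and sets the terms of the point.

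**The stakes are small.** This also stands. Assuming an overall alpha of 0.05, the corrected threshold is 0.05/7 = 0.0071 (z = 2.69). A bias of 0.28 standard errors raises the false-positive risk only to about 0.0080 + 0.0015 = 0.0095.

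**The number 46 is ambiguous.** A reader might infer that the analysis is restricted to people measured at both visits. The wording can equally be a visit schedule for those enrolled, and the same paragraph claims intention-to-treat. The point does not depend on the reading: non-attenders either add only a baseline or are left out.

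**Imputation can do harm.** This stands for one tempting specification, by-arm imputation with the last weighing day as a predictor. If attenders all weigh until near day 84, the coefficient for day is barely estimable and is extrapolated to early stoppers. In two simulations on assumed weight paths at n = 46, it raised the sampling SD of the fat-mass effect from 0.78 kg to 1.78 kg and 1.97 kg. Without the day term, imputation cut the bias from about −0.28 to −0.05 kg and the SD from 0.78 to 0.75 kg.

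**It should not cover all seven outcomes.** Agreed. A reader might extend the gain to glucose, insulin, HbA1c or energy expenditure, but the documents give no basis for that.

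**A likelihood mixed model is standard, and this is a pilot.** True, but with one follow-up visit its missing-at-random protection conditions on baseline alone, and better information is already collected.

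**Conclusion.** The point holds in conditional form. The secondary model has no protection against attendance that depends on weight change, although the trial collects the data that would supply it for body fat and lean mass. If that dependence differs by arm, the effect labelled intention-to-treat is biased. If missed visits are unrelated to weight change, the bias is about zero.

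Under the assumed patterns the bias stayed below the full-data standard error of 0.29 SD, except in the most extreme case (opposite directions by arm, r = 0.8, 30% missed), where it reached 0.40 SD. Its actual size cannot be determined from the documents. This is an inexpensive improvement to two outcomes. It does not show that the planned analysis is invalid, and it does not bear on the primary outcome.

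**What to change.** 1. Define the secondary analysis set as every local randomised participant with a baseline clinic visit, whether or not week 12 is attended, and say what the 46 counts.
2. For body fat and lean mass, pre-specify multiple imputation of missing week-12 values from arm, baseline value and home-scale weight change. Choose the weight summary in advance, for example the last available 7-day mean or the participant's fitted slope. Do not add the last weighing day as a separate predictor. Then run the planned interaction analysis with the Bonferroni correction for 7.
3. Report this alongside the planned mixed model for those two outcomes, and state the missing-data assumption behind each.
4. Keep the planned mixed model as the main analysis for glucose, insulin, HbA1c, resting metabolic rate and total energy expenditure.

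The cost is SAP wording and a little programming, with no new data or visits. The correction is weaker when home weighing stops early, and it cannot reach attendance that depends on changes after weighing has stopped.

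### The model for the clinic outcomes gives each randomised arm its own baseline mean, which is valid but usually less precise than baseline adjustment in a 46-person subset

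*Combined protocol and SAP*

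**What the plan says.** The secondary-outcomes paragraph of the Statistical Analysis Plan lists body fat, lean mass, fasting glucose, insulin, HbA1c, resting metabolic rate and total energy expenditure, "assessed at the baseline and 12-week clinical visits for a subset of 46 participants". They are to be analysed by "LMMs with fixed effects for treatment assignment, an indicator for the 12-week visit, and their interaction, and a random effects for participant", and "The treatment effect will be estimated by the interaction". P-values and intervals are Bonferroni-corrected for seven comparisons. The remaining clinic outcomes are exploratory and are "analyzed using the methods described for the secondary outcomes, without penalization for multiple comparisons".

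On timing, Experimental Design says "Immediately prior to study start, participants will go to the Clinical and Translational Science Institute (CTSI) clinical research center" for the baseline measurements, and "After 12 weeks, participants will come to the CTSI clinic to repeat the baseline measurements". It also says "Participants will be randomized to one of two eating plans" and "Group allocation will be provided to subjects using the Eureka mobile research platform", but not whether a participant's allocation was shown before or after the clinic baseline.

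**The concern.** With two arms and two visits, the planned fixed effects fit all four arm-by-visit means freely. The treatment main effect is then a baseline difference between arms, estimated from the data. If baseline was measured before allocation was known, randomisation makes that difference zero in expectation, and the plan makes no use of this. The SAP contains neither a baseline covariate nor a constraint to a common baseline mean.

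The planned estimate therefore carries the whole of any chance baseline imbalance into the comparison of changes, whereas an adjusted model removes the predictable part. What is at stake is precision where it is scarcest: 46 people, with each secondary test at 0.05/7 = 0.0071 (taking a two-sided 0.05 family level, which the SAP does not state). The primary weight analysis is not affected.

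**Working it through.** **Inputs.** From the SAP: 46 participants, two visits, the model terms and the Bonferroni factor of 7. Assumed, because the documents do not give them: 23 per arm, complete pairs, two-sided 0.05 before correction, the correlation ρ between baseline and 12 weeks, and the effect size. The SDs at the two visits are taken as equal (σ) unless stated. The documents give no power or precision figure for these outcomes, so there is none to reproduce.

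**Step 1: what the planned model estimates.** In a simulated data set of 46 complete pairs, a REML fit of the planned model gave an interaction of 0.2328 with SE 0.2096. The difference in mean change gave the same estimate and SE.

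**Step 2: variances.**
- Planned: 2σ²(1−ρ)(2/23).
- Baseline-adjusted (ANCOVA): σ²(1−ρ²)(2/23)(1+1/42). The last factor is the cost of estimating the slope, with 42 = 46−4.
- Ratio, adjusted to planned: (1+ρ)/2 × 1.0238.
- Break-even: ρ = 2/1.0238 − 1 = 0.953. Above it the loss is at most 1/42 = 2.4% of variance.

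| ρ | Planned variance (σ²) | Adjusted variance (σ²) | Ratio | 46 ÷ ratio | Detectable difference at 80% power, planned → adjusted (SD) |
|---|---|---|---|---|---|
| 0.5 | 0.0870 | 0.0668 | 0.77 | 60 | 1.09 → 0.95 |
| 0.7 | 0.0522 | 0.0454 | 0.87 | 53 | 0.84 → 0.79 |
| 0.8 | 0.0348 | 0.0320 | 0.92 | 50 | 0.69 → 0.66 |
| 0.9 | 0.0174 | 0.0169 | 0.97 | 47 | 0.49 → 0.48 |

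Simulation (40,000 trials per ρ) gave ratios of 0.76, 0.92, 0.97, 1.00 and 1.01 at ρ = 0.5, 0.8, 0.9, 0.95 and 0.98.

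**Step 3: power** at two-sided 0.05/7, from the noncentral t with 44 df (planned) and 43 df (adjusted):

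| True effect | ρ = 0.5 | ρ = 0.7 | ρ = 0.8 | ρ = 0.9 |
|---|---|---|---|---|
| 0.8 SD | 46 → 61% | 75 → 82% | 92 → 94% | 99.9% both |
| 0.5 SD | 14 → 20% | 28 → 33% | 45 → 49% | 83 → 84% |
| 0.3 SD | 4 → 6% | 8 → 9% | 13 → 14% | 31 → 32% |

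With an 18/28 split, power for 0.8 SD goes from 44 to 58%, 72 to 79% and 91 to 93% at ρ = 0.5, 0.7 and 0.8, so the result does not depend on equal arms.

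**Step 4: unequal SDs.** Let k be the 12-week SD divided by the baseline SD. Before the slope cost, planned minus adjusted variance is proportional to (1+k²−2ρk) − k²(1−ρ²) = (1−ρk)², which is never negative. With the slope cost, the ratio is 0.585 (ρ 0.5, k 0.8), 0.655 (0.8, 0.8), 0.914 (0.5, 1.25) and 1.024 (0.8, 1.25). In the last case ρk = 1 and only the slope cost remains.

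**Step 5: a chance imbalance.** The SD of the baseline difference between arms is √(2/23) = 0.29 outcome SD. An imbalance of that size shifts the planned estimate by (1−ρ) × 0.295 = 0.15, 0.09, 0.06 and 0.03 SD at the four ρ values, or 0.50, 0.39, 0.32 and 0.22 of its SE. Over repeated trials this averages to zero, and the planned SE already includes it.

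**Step 6: type I error.** In the 40,000-trial simulations both analyses were unbiased and rejected 4.9 to 5.1% at nominal 5%. At nominal 0.0071, null trials with ρ of 0.5 and 0.8 and k of 0.8, 1.0 and 1.25 (12,000 per setting) gave:
- planned model: 0.0070 to 0.0082;
- ANCOVA: 0.0059 to 0.0083;
- common baseline mean with only a random intercept: 0.0025 to 0.0030 (k 0.8), 0.0067 to 0.0077 (k 1.0) and 0.0148 to 0.0159 (k 1.25). At k 1.25 its nominal 5% test rejected 7.4 to 7.8%.

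A smaller check (4,000 null trials per setting) of the common-baseline model with unstructured covariance gave 0.006 to 0.009 with Satterthwaite degrees of freedom, but 0.0095 to 0.0135 with normal critical values.

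**The case against.** The strongest reply is that nothing here is wrong. The SAP sets out to estimate an effect on changes, the interaction does exactly that, and the choice lies between two legitimate prespecified analyses in a study described as a pilot. The benefit rests on a correlation that the documents do not give. At ρ of 0.8 or more, power rises by at most about 4 points, and for a 0.3 SD effect it stays at or below 32% under either model. Body fat and lean mass by DXA may track so closely over 12 weeks that they gain nothing. The common-baseline model also needs equal expected baselines, which the text does not secure because the timing of allocation relative to the clinic visit is unstated. Finally, it is easier to implement badly than the planned model.

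Most of this stands as a limit on size and urgency. It does not remove the point. The baseline values are already collected, the worst loss with equal SDs is 2.4% of variance, and at ρ = 0.5 the gain is worth about 14 participants. The implementation risk is real, so the covariance structure and the degrees-of-freedom method must be named. The timing question is a condition on the change. Confirming that baseline came before allocation also settles entry to the subset, since anyone measured by then had already joined. The figures assume complete pairs, and dropout in the subset is unknown.

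**Conclusion.** The concern holds as a matter of efficiency. The planned model for the secondary and exploratory clinic outcomes is valid, but it ignores the equality of baselines that randomisation provides. Under the stated assumptions it gives up 23%, 13%, 8% and 3% of variance at ρ = 0.5, 0.7, 0.8 and 0.9, and nothing from about 0.95 upward. The algebra is secure. The gain for any named outcome is not, because ρ and the visit SDs are unknown. The change is worth making before the data are seen, because choosing an adjusted model afterwards would be open to question. It is a recommended improvement, not a correction the trial cannot do without.

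**What to change.** Prespecify one baseline-adjusted model for the secondary and exploratory clinic outcomes.

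- **Preferred:** an LMM with a common baseline mean, a 12-week indicator and a treatment-by-12-week term, without the treatment main effect. Use an unstructured 2×2 within-person covariance and a named small-sample degrees-of-freedom method, such as Satterthwaite. Like the planned model, it keeps participants who miss one visit.
- **Avoid:** dropping the main effect while keeping only the random intercept. That test relies on equal SDs at the two visits, and in simulation its error rate about doubled when the 12-week SD was 1.25 times baseline.
- **Alternative:** ANCOVA of the 12-week value on arm and baseline. With complete data its point estimate matches the preferred model, but it drops anyone missing either visit, so the SAP should name one of the two.
- **Condition:** state whether the clinic baseline was measured before allocation was released. If this cannot be confirmed, keep the planned model as the main analysis and report the adjusted one as a sensitivity analysis.

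The cost is one fixed effect removed, one covariance parameter added, a named degrees-of-freedom method and one sentence on timing. No new data are needed. Estimating the slope costs about 2.4% of variance (1/42), which the ratios above already include.
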